This is a multi-wave study, with approximately all the participants recruited by the end of Year 02 and the remainder in the beginning of Year 03. At baseline, we will conduct comprehensive assessments of all study constructs and repeat all other assessments annually. Activities during the first three months will consist of the following: Staffing, Instrument Calibration, Ethnographic Update. Each wave will be composed of 22 participants to be randomized into two groups (11 each). Each undergo assessment at intake (T1) and outtake (T2), a booster session 3 months after outtake and a final assessment at 12 months. Data analysis process will be initiated at the third month and continue throughout the study implementation.

Study Protocol

[figure not shown]
IRB ID: 20180597 (CR00012479)

Study Number: 1 R34 DA043784-01A1

Date: July 19, 2018

Publications are expected to start from month 20. The table below details the activity processes.

Project Timeline

9) Study Endpoints*

Primary outcomes are: intervention attendance and completion; sustained abstinence in substance use through biochemical verification and self-report; family functioning; sexual risk behavior; and conduct disorder.

Secondary outcomes include recidivism in delinquency, improvement in family communication, and peer/gang involvement.

10) Procedures Involved*

RCT procedures

CIFFTA has three major components – Family-Based Therapy, Individual Therapy, and Psycho-educational Modules – delivered over 16 weeks in a six sessions (60 minutes each) per month format. In this study, the therapy will be delivered in the home to reduce missed sessions and premature termination. Special training will focus on how to structure the home environment to reduce distractions. Three sessions per month will typically be a session which may include Family-based Therapy or Psycho-educational modules with the family or parents alone (e.g., parent training). The other three sessions are typically with the adolescent alone and include Motivational Interviewing or Psycho-educational modules designed for the adolescent.

Study Protocol

IRB ID: 20180597 (CR00012479)

Study Number: 1 R34 DA043784-01A1

Date: July 19, 2018

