Youth Urine Toxicology. As part of our research component, we plan to collect voluntary urine specimens for analysis at the times of the youths' initial and follow- up interviews in order to validate self-report. We will follow procedures informed by NIDA's CJDATS workgroup guidelines. Urine specimens will not be collected on youths incarcerated for more than two days. The use of four substances will be probed using the Onsite CupKit® urine screen procedure (positive threshold levels are noted in parentheses): (1) methamphetamines (500 nanograms per milliliter [ng/ml] of urine), (2) opiates (300 ng/ml of urine), (3) cocaine (300ng/ml of urine), and (4) marijuana (THC) (50 ng/ml of urine). The surveillance window for the four drugs is as follows: methamphetamines and opiates = 48 hours; cocaine = 72 hours; marijuana: moderate users = 5 days; heavy users = 10 days; chronic users = 20 days. Although we considered hair analysis, urine screens were selected because of they are the most widely used and accepted method for supervision monitoring (Lipsey & Wilson, 1998), they are minimally invasive, can be collected in the community during follow-up assessments and carry fewer taboos on collection (Meyers et al., 2002). Urine screen results will be kept confidential, and will be collected in containers marked with pre-printed labels without personal identifying information. To assure integrity of the sample, the Onsite CupKit® automatically checks for temperature, and the interviewer will ensure that there is no one else in the restroom.

Overview of Assessment Procedures and Attrition

The 3-month follow-up assessment will be measured from the end of the intervention, as will be the 6-month and the 12-month follow-up

Study Protocol

IRB ID: 20180597 (CR00012479)

Study Number: 1 R34 DA043784-01A1

Date: July 19, 2018

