& Wilson, 1998), they are minimally invasive, can be collected in the community during follow-up assessments and carry fewer taboos on collection (Meyers et al., 2002). Urine screen results will be kept confidential in containers marked with pre-printed labels without personal identifying information. To assure integrity of the sample, the Onsite CupKit® automatically checks for temperature, and the interviewer will ensure that there is no one else in the restroom.

Study Protocol

IRB ID: 20180597 (CR00012479)

Study Number: 1 R34 DA043784-01A1

Date: July 19, 2018

12) Data Management*

Qualitative data:

Research staff will be monitored during every step of data collection by appropriate investigators. Instruments will be reviewed periodically to insure validity and reliability. Data will be entered by our personnel into a database under the supervision of PI. Control measures will be instituted to ensure accuracy of data entry procedures prior to analysis. Also, all data will be analyzed at our data processing center, under guidelines of our data safety and monitoring plan. All written and tape-recorded materials in this study will be transcribed using Microsoft Word on a daily basis and stored in locked the PI files cabinet. They will be coded and analyzed using procedures described in Schensul et. al.

The PI, with the assistance of the project's co-Is and Post-Doctoral Associate, will analyze the data using SPSS®, STATA®, the R statistical package or relate statistical software. Outcome measures will include drug use, delinquency/crime, family functioning, educational performance, and emotional/ psychological functioning. Predictor and outcome data will be analyzed using confirmatory factor analysis, generalized linear mixed effects modeling, latent growth modeling, structural equation modeling, analysis of variance, logistic regression, and stepwise multiple regression. The significance levels will be adjusted to control for multiple outcome measures. For the primary hypotheses, power is anticipated to be .80.

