based research in the Haitian community in Miami-Dade. All research clinical staffs have been performing CIFFTA in diverse ethnic contexts in Miami-Dade for over two decades. They are well-trained in human subject protection and research implementation. They are well-informed of their tasks and duties and they will be trained for this study to be implemented in the Haitian community. The 88 at-risk youth (ages 13-16) of Haitian descent will be recruited in Miami-Dade County with the intention to analyze 80 participants because of attrition. Sample sizes are derived from power calculations based on data from published work.

Two therapists will deliver the CIFFTA intervention. Therapist will have experience in working with adolescents with behavior problems and with Haitian families. The first phase of therapist CIFFTA training will consist of a 3-day training workshop that includes the use of didactic material, the intervention manual, and the presentation of videotaped sessions from our previous CIFFTA work. This workshop will also include presentations by the PI and [name] on what is known about Haitian families in our community. The second phase will include intervention implementation with 1 pilot case. A therapist is required to work with a pilot case over at least a one-month period and work with that pilot cases will be supervised directly by the study PI, the CIFFTA Developer, and the CIFFTA supervisor. Because the implementation of the psycho-educational modules is fairly straightforward, training and certification efforts will focus primarily on the individual and family-based therapy components. Any rating below "adequacy" will require retraining on that specific component.

Interventions will be delivered over a briefer period than is typical of the actual intervention in the trial but will be sufficient to ensure comfort and competence in the key intervention components. There will be a 2 day workshop following the pilot phase to solidify any issues that remain and to incorporate any manual clarification that will assist in achieving high levels of competence and fidelity/adherence. This training format has been utilized successfully in our family training institute. SOC therapists will already be experienced in delivering the community standard and will not require additional training.

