### ***Analytic Methods***

Latent Growth Modeling within a Structural Equation Model (SEM) framework. We will conduct latent growth curve analyses using Stata 14 gsem (1), SAS Proc Mixed (2), SPSS Mixed Models, and/or Mplus 8 (3) to compare the trajectories of participants in CIFFTA to those in TAU. Given that the data are balanced and have more than 2 time points, the model is identified, thereby allowing us to perform SEM growth curve analysis (4). These models conceptualize each component of growth (the baseline/intercept, the slope/rate of change, the quadratic slope, etc.) as composed of a fixed and random effect. Thus, these models have multiple components of variance as well as a regression-type model of the underlying mean growth curves of the two groups. Within an SEM framework, growth curves are treated as latent (unobserved) variables influenced by occasion- and individual-level covariates, allowing us to explicitly model growth trajectories overtime.

Specific analysis link functions will be matched to fit the distribution of each outcome variable. For ordinal outcomes (e.g., frequency of drug/alcohol usage), we will use an ordinal logistic regression function. The proportional odds assumption will be evaluated using the Brant test, and if needed, addressed by allowing problematic coefficients to vary across levels of the outcome variable. Count outcome measures (e.g., number of sexual partners, problem behaviors, re-arrests) will be analyzed using a negative binomial function rather than Poisson regression to address potential over-dispersion. Vuong tests will be performed to assess whether the data have an excess of zeros, and if necessary, zero inflated negative binomial regression will be used instead.

Analysis for Aims 2 and 3: The first set of analyses will explore the efficacy of CIFFTA compared to SOC in modifying the main adolescent outcomes and to generate effect sizes for a possible full clinical trial: a) drug/alcohol use, b) risky sexual behavior, c) delinquent behavior, and d) recidivism. Latent growth modeling will be used to investigate the efficacy of CIFFTA as compared to SOC. For each model, we will examine the effect sizes to determine the overall impact of CIFFTA over SOC on the outcome variables. We will generate estimates of effect sizes, such as Cohen's d (5), for both rate of change and for the

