**Power Analysis:** We will recruit 88 participants for this study, with the intention of analyzing data for 80 participants after attrition. The original CIFFTA randomized trial with 28 Hispanic adolescents showed CIFFTA to be more efficacious than the comparison family treatment at: 1) reducing drug use, and 2) improving parenting practices as reported by adolescents (7). More recently, a technology assisted CIFFTA study of 80 minority youth at high risk for drug use showed CIFFTA to be more efficacious in reducing behavior and conduct problems and in improving family cohesion, when compared to a delay treatment condition (8). Based on these findings, CIFFTA was placed on the National Registry of Evidence Based Practices using their more rigorous criteria for entry. Given such consistent findings of efficacy for CIFFTA among Hispanic youth, a sample size of 80 will be sufficiently powerful to detect relatively small effects ( $R^2 = 0.05$ ) at adequate levels of power (0.84 - 0.86) using a relatively simple SEM. A sample size of 80 is also well above sample guidelines for Stage 1 treatment trials (80)). Nevertheless, to deal with attrition, which in the case of Haitian and because of the ethnographer's engagement with the families will not be higher than 10%, we plan a sample of 88 adolescents.

Nevertheless, we recognize and appreciate the limits of estimating simple SEMs, such as ours, with a small sample size. Therefore, we will take several steps to mitigate concerns about statistical power, including: limiting the use of latent variables when possible, constructing parsimonious path models, and using Bayesian estimators. When theoretically and empirically appropriate, we will use principal components factor analysis to combine multiple indicators into a single scale capturing the underlying construct rather than estimating multiple latent variables since the latter often requires larger samples.

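### The SAP's power of 0.84-0.86 for R² = 0.05 with 80 youths does not follow from its stated inputs, which give about 0.53 in a simple two-arm test

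*SAP*

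**What the plan says.** The SAP (Analytic Methods, Power Analysis) plans 88 recruited and 80 analysed. It states that 80 "will be sufficiently powerful to detect relatively small effects ( $R^2 = 0.05$ ) at adequate levels of power (0.84 - 0.86") with a fairly simple SEM, and introduces this by citing earlier efficacy findings without quoting any estimate from them. It then acknowledges the limits of fitting SEMs to a small sample and calls the analyses preliminary.

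The protocol bears on the figure in several places:

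- 22) Resources Available: "Sample sizes are derived from power calculations based on data from published work".
- 12) Data Management: "For the primary hypotheses, power is anticipated to be .80", with no effect size or alpha, and "The significance levels will be adjusted to control for multiple outcome measures", with no level or rule.
- 8) Study Timelines, on allocation: "Each wave will be composed of 22 participants to be randomized into two groups (11 each"). The SAP's Analysis Rationale gives four waves, so 4 × 22 = 88, or 44 per arm, with 40 per arm analysed.
- 8) Study Timelines, on visits: "Each undergo assessment at intake (T1) and outtake (T2), a booster session 3 months after outtake and a final assessment at 12 months". Sections 3 and 10 instead list follow-ups at 3, 6 and 12 months, and section 10 fixes their origin: "The 3-month follow-up assessment will be measured from the end of the intervention".

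On the model, the SAP specifies latent growth curves with random effects, and effect sizes for the rate of change and for the between-arm difference at a given time. Several main outcomes are not continuous: "For ordinal outcomes (e.g., frequency of drug/alcohol usage), we will use an ordinal logistic regression function", and counts are to be modelled as negative binomial.

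**The concern.** Once N, the effect, alpha and the test are fixed, power is determined. The SAP fixes N = 80 and R² = 0.05 and reports 0.84-0.86, but the available text leaves out the rest. Earlier efficacy findings could justify choosing an effect size. They cannot raise the power for an effect already set at R² = 0.05.

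The protocol says that the sample size comes from power calculations, and this is the only power figure in the available text with an effect size attached. If a reader believes 0.85 when the power may be nearer 0.5, a non-significant pilot result looks like evidence against an effect that the pilot could easily have missed. Nor can the figure be carried into planning the full trial while its inputs are unknown.

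**Working it through.** **Inputs from the documents.** 80 analysed; 1:1 allocation, so 40 per arm; R² = 0.05.

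**Assumptions not in the documents.** Two-sided alpha of 0.05 unless noted; R² is the arm contrast; continuous normal outcome with SD 1; correlation r between any two visits of one youth.

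**1. Trying to reproduce 0.84-0.86.** Cohen's f² = R²/(1 − R²) = 0.05/0.95 = 0.0526. With 1:1 arms, d = 2√0.0526 = 0.459. The noncentrality is λ = N × f² = 80 × 0.0526 = 4.21. The test is F with 1 and 78 df.

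| Setting | Power |
|---|---|
| N = 80, two-sided 5% | 0.527 |
| N = 80, one-sided 5% | 0.652 |
| N = 80, two-sided 20% | 0.777 |
| N = 88, two-sided 5% | 0.567 |
| N = 168 | 0.840 |
| N = 178 | 0.861 |

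Joint tests of 2 to 5 predictors at N = 80 give 0.42 down to 0.29. Reading 80 or 88 as the number per arm gives 0.82 or 0.86, but that contradicts four waves of 22. With 80 analysed, this test has 80% power at R² = 0.091 (d = 0.63).

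**2. Longitudinal and adjusted models.** All use d = 0.459 and 40 per arm.

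- Difference at one time, baseline-adjusted: residual variance 1 − r², λ = 20d²/(1 − r²).
- Constant effect averaged over three follow-ups, baseline-adjusted: variance (1 + 2r)/3 − r².
- Rate of change: gap rising linearly from 0 at baseline to 0.459 at the last visit, λ = d²/Var(slope difference) by generalised least squares, no random slopes. Outtake is at 16 weeks (3.7 months), so follow-ups counted from the end of the intervention fall at 6.7, 9.7 and 15.7 months.

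| Contrast | r = 0.3 | r = 0.5 | r = 0.7 |
|---|---|---|---|
| One time, baseline-adjusted | 0.565 | 0.648 | 0.810 |
| Slope, baseline + 3, 6, 12 months, free baselines | 0.415 | 0.542 | 0.760 |
| Same, equal baseline means | 0.634 | 0.686 | 0.830 |
| Slope, as above plus outtake, free baselines | 0.454 | 0.588 | 0.804 |
| Same, equal baseline means | 0.637 | 0.701 | 0.853 |
| Slope, intake, outtake, 12 months after outtake, free baselines | 0.433 | 0.563 | 0.781 |
| Same, equal baseline means | 0.565 | 0.653 | 0.824 |
| Constant effect, mean of three follow-ups | 0.861 | 0.881 | 0.953 |

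Counting the final visit at 12 months from intake gives 0.419/0.546/0.764 with free baselines and 0.568/0.648/0.815 with equal ones.

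For the single-time and slope contrasts, 0.84 needs r of about 0.69-0.76, depending on contrast and schedule. Only one cell at r ≤ 0.7 reaches it.

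**3. Random slopes.** The SAP plans them. An assumed slope SD of 0.3 outcome SDs lowers the best slope row (0.637/0.701/0.853) to 0.589/0.646/0.785. Across all the slope cases the range becomes about 0.39-0.79.

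**4. Covariate route.** If R² = 0.05 is instead an increment in total variance, f² = 0.05/(0.95 − c), where c is the share explained by other covariates. Power of 0.84 needs c = 0.503 and 0.86 needs c = 0.528. With d fixed at 0.459, the same shares give 0.820 and 0.839.

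**5. Multiplicity, illustration only.** Bonferroni over the SAP's four main outcomes gives alpha = 0.05/4 = 0.0125. The simple test falls to 0.313, and the single-time and slope contrasts of step 2 to 0.22-0.69.

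**6. Ordinal outcome, illustration only.** A latent shift of 0.459 at one time, unadjusted, with four categories, was simulated 20,000 times per case under logistic and normal latent distributions. Power was 0.46-0.54 with even categories, 0.32-0.33 with 70% of controls in the lowest category, and 0.25-0.26 with 80%.

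**The case against.** The strongest reply is that 0.53 is the power of a test the SAP does not plan, at an alpha the documents do not give. The SAP ties its figure to an SEM with repeated measures, and such a model can reach 0.84-0.86. This stands as a limit: no arithmetic slip inside the sponsor's calculation has been shown, and 0.53 is only a reference value. It does not rescue the figure, because reaching it needs a high within-person correlation, a large covariate R² or a constant effect averaged over visits, and none of these is stated.

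The illustrative ranges are also open to challenge. The slope values in step 2 omit the random slopes that the SAP plans; including them lowers power further. R² could mean explained latent-slope variance, or refer to a mediated path or the change index that the SAP also tests, so the ranges do not cover every reading. The planned Bayesian estimators are not modelled. The ordinal distributions and the Bonferroni rule are invented for illustration. These points limit how far the ranges can be pressed, and they show that the tested parameter has to be named.

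Finally, this is a pilot: the SAP calls its analyses preliminary, and its stated output for a full trial is effect sizes rather than this power figure. That is fair, and it confines the harm to interpretation and planning. The caveats neither supply the missing inputs nor withdraw the number.

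**Conclusion.** The concern holds. The stated inputs give a power of about 0.53 in a simple two-sided 5% test, about 0.31-0.33 below the claim, and that test would need roughly twice the planned number analysed. For the two named effect-size contrasts, power is about 0.41-0.85 without random slopes at r = 0.3-0.7, and mostly below 0.84. True power is undetermined because its inputs are not stated, so 0.84-0.86 is unsupported rather than proved impossible.

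If R² = 0.05 is the arm contrast, calling it relatively small is loose: d of about 0.46 lies close to the SAP's medium benchmark of 0.5. The protocol's .80 has the same gap.

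This rests on R² being the arm contrast, on a continuous outcome except where noted, and on assumed correlations and effect shapes. Part of the SAP was not in the text available for review. The sample size itself is not in question.

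**What to change.** Keep 88 recruited and 80 analysed. Reconcile the visit lists in protocol sections 3, 8 and 10 first, because growth-model power depends on them. Then replace 0.84-0.86 with a figure for one named contrast, for example:

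> With 80 analysed (40 per arm), alpha [x], [one/two]-sided under [multiplicity rule], the [named contrast] on [outcome, type] has power [y] for [effect], assuming visits [list], within-person correlation [r] and covariate R² [c], from [source].

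Give a range over r if there is no source. State any random-slope variance. For an ordinal or count outcome, compute power under that model and state the assumed category distribution or dispersion. Keep 0.84-0.86 only if documented inputs reproduce it; otherwise withdraw it.

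Add a labelled reference:

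> For a continuous outcome, an unadjusted single-time comparison at two-sided 5% has power of about 0.53 at R² = 0.05 (d about 0.46) and 80% power at R² of about 0.09 (d about 0.63).

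Say that R² = 0.05 is close to medium on the SAP's scale if it is the arm contrast. Align the protocol's .80 with the recomputed figure, or remove it.

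The cost is one recalculation and wording in two places. The sponsor must settle one contrast, its outcome type, the visit list and a multiplicity rule. The stated power may become less favourable. No extra participants are needed.

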difference at a particular time between the two conditions (6). Following Cohen's guidelines (5), we will interpret our effect sizes using the convention of "small" ( $d = .2$ ), "medium" ( $d = .5$ ), and "large" ( $d = .8$ ).

Our hypotheses concerning the direct and indirect effects of key variables on drugs/alcohol use, risky sexual behavior, delinquent behavior, and recidivism will be tested using SEM mediation analyses. To test potential indirect relationships we will include several mediators, including family connectedness, acculturation (bicultural involvement scale), and motivation to change. This will allow us to examine whether CIFFTA directly effects our outcomes of interest and/or whether the effect of CIFFTA operates through its effect on family connectedness, acculturation, and motivation to change. These mediation models will enable us to address **Specific Aim #2** by testing the significance of paths in the model linking the intervention variable to the risk-related outcomes in question (both at discrete points in time and as the change index derived from differences in ordinal frequency at baseline and at post-intervention time intervals).

In a separate set of analyses, we will examine the hazard rate of drug/alcohol use and sexual risk behavior during the post-intervention phase of the study. Comparisons across the two intervention conditions will thus be made regarding the hazard rate of having sex during the post-intervention period, sex with multiple partners ( $>1$  per month), and unprotected sexual episodes. Specifically, shared frailty Cox proportional hazard regression will be utilized to examine possible differences in the hazard rate of various risky behaviors (drug- and sex-related) in CIFFTA and control conditions during the post-intervention phase. This will prove particularly helpful in determining the hazard rate for post-intervention sexual initiation or unprotected sex in the two groups being compared, while also controlling for the time-dependence nature of our data. Similar analyses will be performed regarding initiation into drug use and other problem behaviors to determine whether the possible benefits of the CIFFTA approach extend to a range of risky behaviors.

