**Analysis Rationale:** While there are numerous approaches to analyzing longitudinal data, including hierarchical linear models (HLM), we opted for a SEM approach since it provides greater modelling flexibility and better enables us to test our underlying theoretical model. In contrast to HLM, SEM allows for the simultaneous estimation of multiple growth curves, indirect/direct effects, and multiple indicators of model fit. Mediating relationships can be assessed within a HLM framework using Baron and Kenny's (10) approach, but SEM allows for the decomposition of direct/indirect effects as well as the simultaneous estimation of mediating and moderating relationships (11). Moreover, SEM will allow us to estimate growth-curves and mediating relationships at the same time in a way that HLMs cannot (12). The estimation of indirect effects within a growth-curve framework is especially important for **Specific Aim #2**, as we hypothesize that CIFFTA will not only have a direct effect on our outcome measures, but will also have an indirect effect operating through its effect on family connectedness, acculturation, and motivation to change. The estimation of mediating relationships will provide greater insights into any causal mechanisms (if any) at work, allowing for a more refined application of CIFFTA in a possible full clinical trial. SEM is also better equipped for assessing our theoretical model. In addition to providing measures of statistical significance, SEM generates several useful measures of overall model fit (e.g., CFI, AIC, BIC, etc.) that can be used to evaluate the appropriateness of our theoretical model over alternative models (11). Finally, SEM is better equipped to handle missing data than traditional regression or HLMs as it allows for maximum likelihood or Bayesian estimation (13).

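### The SAP's power of 0.84-0.86 is not tied to a stated parameter and does not describe the power of the two-path indirect effects that the same SEM tests

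*SAP*

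**What the plan says.** The SAP has one quantified power statement, in its Power Analysis paragraph. The sample is planned "with the intention of analyzing data for 80 participants after attrition", from 88 recruited, and is described as "sufficiently powerful to detect relatively small effects ( $R^2 = 0.05$ ) at adequate levels of power (0.84 - 0.86) using a relatively simple SEM". No alpha, sidedness or model equation is given, and the parameter with R² = 0.05 is not named.

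The analysis goes beyond a comparison of arms. Under Analytic Methods the SAP commits to mediation models fitted by SEM: "Our hypotheses concerning the direct and indirect effects of key variables on drugs/alcohol use, risky sexual behavior, delinquent behavior, and recidivism will be tested using" such models. Three mediators are named (acculturation, motivation to change, family connectedness), and the models are assessed through the significance of their paths. The Analysis Rationale adds: "The estimation of indirect effects within a growth-curve framework is especially important for Specific Aim #2". No power is given for an indirect effect.

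The SAP does acknowledge the limits of a small sample. It lists mitigations (fewer latent variables, parsimonious or separate path models, Bayesian estimators) and calls its analyses preliminary. The Protocol, under Data Management, gives a different figure, .80 for the primary hypotheses, and says that significance levels will be adjusted for multiple outcomes.

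**The concern.** A single R² ordinarily describes one path, or one set of predictors of one outcome. An indirect effect is a product of two paths: arm to mediator, and mediator to outcome given arm. If it is judged by whether both paths are significant, its power cannot exceed that of the weaker path. One R² with one power figure therefore does not determine it; the sizes of both paths are needed.

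The Power Analysis moves straight from the 0.84-0.86 statement to a discussion of path models and mediating relationships, so the figure reads as if it covered them.

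The mediation results are meant to inform how CIFFTA is applied in a full trial. A reader who believes that power is about 0.85 may give a non-significant indirect path more weight as evidence against a mechanism than the sample can support.

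**Working it through.** **Inputs from the documents.** N = 80 analysed (SAP, Power Analysis); 1:1 allocation (Protocol, Study Timelines: 11 and 11 per wave of 22), so 40 per arm; R² = 0.05; stated power 0.84-0.86.

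**Assumptions, because the SAP is silent.** Two-sided alpha 0.05, one mediator, no gain from covariates or repeated measures, least-squares path tests, and the indirect effect declared when both paths are significant.

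**Step 1: the printed figure.** For one coefficient, f² = R²/(1 − R²) = 0.05/0.95 = 0.0526. The noncentrality is N × f² = 80 × 0.0526 = 4.21. With 1 and 78 degrees of freedom the power is 0.53. As a two-arm mean difference, d = 2 × √0.0526 = 0.459, and 40 per arm gives 0.54.

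Variants of the single-effect calculation:

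| Variant | Power |
|---|---|
| One-sided 0.05, N = 80 | 0.65 |
| Two-sided 0.05, N = 88 | 0.57 |
| One-sided 0.05, N = 88 | 0.69 |
| Two-sided 0.20, N = 80 | 0.78 |

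None reaches 0.84-0.86. At R² = 0.05 and two-sided 0.05 that power needs N of about 168-178; at N = 80 it needs R² of about 0.10-0.106. It can be reached with gains that the SAP does not state: covariates explaining about 50% of the outcome variance (0.84), the mean of three follow-ups correlated 0.2 (0.85), or the mean of four measures correlated 0.3 (0.85).

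**Step 2: indirect effect from the SAP's literal inputs.** Joint-significance power is roughly power(path 1) × power(path 2). With R² = 0.05 on both, 0.53 × 0.53 = 0.28. Simulation gives 0.25-0.27, depending on how the second path's R² is defined (20,000 runs of M = aX + e, Y = bM + e; one run gave path powers of 0.525 and 0.485, joint 0.249). A Monte Carlo interval for the product gives about 0.25 and a Sobel test about 0.10.

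**Step 3: strengthen only the second path.** Arm to mediator stays at R² = 0.05.

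| Mediator-to-outcome R² | Joint power |
|---|---|
| 0.15 | 0.50 |
| 0.25 | 0.52 |
| 0.50 | 0.52 |

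Power levels off at that of the first path.

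**Step 4: accept the printed figure for each of two equal paths.** 0.84² = 0.706 and 0.86² = 0.740. Simulations with path powers near those values give 0.69-0.73 for joint significance and 0.67-0.74 for the Monte Carlo interval. The range is about 0.67-0.74.

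**Step 5: read R² = 0.05 as a total effect that is fully mediated.** Then R²(a) × R²(b) = 0.05.

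| R²(a), R²(b) | Indirect-effect power |
|---|---|
| 0.5, 0.1 | 0.54 |
| 0.1, 0.5 | 0.84 |
| 0.224, 0.224 | 0.98 |

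Total-effect power is about 0.53 in all three. On this reading, power for the indirect effect can be above or below the printed figure, depending on a split that the SAP does not give.

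**The case against.** The strongest reply is that the SAP never assigns R² = 0.05 to a single path. It speaks of effects in the plural and of an undefined simple SEM, so the single-effect reading is an inference. That stands, and it is why the point is worded as what the figure appears to describe. It does not rescue the figure: Step 5 shows that under the alternative reading it still does not fix the power of an indirect effect.

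A reader might infer that 0.71-0.74 is the best the mediation tests can achieve. The documents do not support that. The range assigns the printed power to each path, which the SAP does not do, and Step 5 gives values up to 0.98. Nor is 0.52 a general ceiling. It holds in the plain two-arm model with R² = 0.05 for arm to mediator, and the planned growth models might gain precision.

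A reader might also infer that a real mechanism will probably be missed. That follows from the 0.25 scenario (a 75% miss rate), not from 0.71-0.74 (26-29%). Nor does the SAP say that a non-significant path will be taken as no mechanism or used to drop a mediator; this is a risk of interpretation, not a documented plan.

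Finally, the SAP calls its analyses preliminary and lists mitigations. This softens the consequence. But no mitigation is quantified, and the SAP presents its path models as theory-led rather than exploratory, so the wording does not correct the figure.

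**Conclusion.** The concern holds in a limited form. The power statement does not name its parameter, alpha or model, does not reproduce for a plain single effect at its own N and R² (about 0.53 under two-sided 0.05), and does not describe the power of the indirect effects to which the SAP gives weight under Aim 2.

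Under the assumptions listed, power for an indirect effect is about 0.25 with R² = 0.05 on both paths and about 0.52 when only the second path is strong. The 0.67-0.74 range is an illustration conditional on accepting the printed power for two equal paths. The true value depends on path sizes, the test used and any precision gain from the growth model, none of which the SAP specifies. Any downward adjustment of alpha for multiple outcomes, as the Protocol foresees, would lower these values.

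The point should be corrected before the mediation results are used to design a full trial. It does not put the pilot itself in doubt.

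**What to change.** In the SAP's Power Analysis:

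1. State the parameter, alpha, sidedness and model behind the power figure, and restate it: about 0.53 for a plain two-arm effect at R² = 0.05 and N = 80, unless stated covariate or repeated-measures gains justify more. Reconcile it with the Protocol's .80.
2. Do not apply that figure to indirect effects. Give simulated power for them over a stated range of sizes for both paths, under the test to be used, with every assumption labelled. Keeping 0.84-0.86 for the arm effect while adding 0.52 for an indirect effect would be inconsistent, because the 0.52 comes from a path with the same N and R².
3. Report indirect effects as estimates with confidence or credible intervals, and say that a non-significant indirect path will not be taken as evidence that the mechanism is absent when the full trial is designed.

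The cost is wording and a short simulation, with no extra participants or data. The stated power becomes less favourable.
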